4.2.4 Other Endpoints

4.2.4.1 Definition

The following exploratory variables will be assessed:

Term	Percentage
GDP	85
Inflation	80
Interest rates	75
Central bank	70
Monetary policy	65
Quantitative easing	60
Inflation targeting	55
Central bank independence	85

4.2.4.2 Derivations

CCI

0 1 2 3 4 5 6 7 8 9 10

Frequency

4.2.4.3 Handling of Dropouts and Missing Data

CCI

4.2.4.4 Primary Analysis of Other Endpoint

CCI

4.3 Safety Analyses

The domain safety covers exposure, adverse events, clinical laboratory, vital signs, and ECG. Safety Analyses will be conducted in the Safety Analysis Set.

4.3.1 Exposure

4.3.1.1 Definitions and Derivations

The study treatment will be administered using single injection. Possible reasons of incomplete injection or other abnormal study drug administration will be collected.

Duration of follow up period will be calculated as difference (in days) of date of last contact with participant – date of study treatment + 1 day.

4.3.1.2 Presentation

Data on the injection results will be listed for the Safety analysis set.

Duration of follow up period and cases of IP administration interruption will be summarized by treatment arm.

4.3.2 Adverse Events

Analysis of adverse events described in details in Section 4.2.1

4.3.3 Clinical Laboratory, Blood Sample

4.3.3.1 Definitions and Derivations

The serum chemistry, haematology, coagulation and other laboratory analyses will be performed.

Detailed list of safety laboratory parameters is presented in the CSP, Section 8.2.4.

4.3.3.2 Presentations

Laboratory data will be assessed and presented per parameter, treatment arm and analysis visit in summary tables using descriptive statistics for continuous variables. Changes from baseline in continuous laboratory parameters will be summarized over all participants by treatment arm and visit. Also cross (shift) tables for changes from baseline according to the maximum CTAE grade will be provided for each parameter separately for low and high abnormal results. Listings of all laboratory parameters will be provided.

4.3.4 Vital Signs

4.3.4.1 Definitions and Derivations

The following vital signs (VS) will be measured according to Section 8.2.2 of the CSP: pulse rate, respiratory rate, blood pressure, and body temperature.

For multiple VS assessments on Visit 1 the following rules will be used for analysis:

- If a participant has multiple VS assessments before IMP dosing, then the last assessment before dosing should be used as baseline and included into the table, but all records should be reported in a listing
- If a participant has multiple VS assessments after dosing then:
 - If a participant has record in "10-15 min window after dosing" then this record should be included in analysis as correct assessment
 - If a participant does not have records in "10-15 min window after dosing" then the first post-dosing assessment should be included in analysis

For multiple VS assessments on Visits 2 and 6 the earliest assessment within a visit window will be used for analysis.

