### 1.3.1 Screening, Treatment and Follow-up Activities

Table 1 Schedule of Activities

Procedure	Screening	Treatment and Follow-up Period						
		1	2	3	4	5	6	EDV
Visit	Screening	1	2	3	4	5	6	
Day	-7 to -1	1	8	15	29	91	181	NA
Window (days)	NA	NA	± 3	± 3	+ 3	± 5	± 14	NA
Written informed consent	X							
Verify eligibility criteria	X	X (predose)						
Randomization		X (predose)						
Medical history and demographics (including COVID-19 vaccine status and previous COVID-19 infection)	X							
Full physical examination, including height and weight	X							X
Targeted physical examination based on medical history		X (predose)						
Vital signs	X	X a	X			X		X
Serum chemistry, hematology, coagulation (local laboratory)	X		X		X			X
Troponin, high-sensitivity test (local laboratory)	X b							

Procedure	Screening	Treatment and Follow-up Period						
		1	2	3	4	5	6	EDV
Visit	Screening	1	2	3	4	5	6	EDV
Day	7 to 1	1	8	15	29	91	181	NA
Window (days)	NA	NA	± 3	± 3	+ 3	± 5	± 14	NA
Follicle stimulating hormone c	X							
HIV test	X							
Electrocardiogram (single, to be performed locally if feasible) d	X							
Urine pregnancy test or serum β-hCG (WOCBP only)	X	X e						
Rapid antigen test for SARS-CoV-2 (performed locally)		X f						
Weekly telephone/email/text contacts-monitoring for safety and COVID-19 qualifying symptom					X			
Assessment of AEs				X				X
Assessment of SAEs, MAAEs, and AESIs	X (SAEs)				X (ongoing observation and questioning)			X
Concomitant medications	X				X (ongoing observation and questioning)			X
CCI [REDACTED]		X (predose)			X	X	X	X

Procedure	Screening	Treatment and Follow-up Period						
		1	2	3	4	5	6	EDV
Visit	Screening	1	2	3	4	5	6	EDV
Day	7 to 1	1	8	15	29	91	181	NA
Window (days)	NA	NA	± 3	± 3	+ 3	± 5	± 14	NA
SARS-CoV-2 nAb serum sample h		X (predose)	X	X	X	X	X	X
CCI		X (predose)			X	X	X	X
Study intervention administration		X						
Injection site reaction monitoring		X j	X					
Immediate AEs k		X						

a On dosing day, vital signs will be performed predose and again approximately 10 to 15 minutes after injection. Any abnormal vital signs must be repeated after the participant has been at rest for at least 5 minutes.

b It is acceptable for this to be performed on Day 1 (predose). Test results must be available prior to dosing.

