4.2.1.3	19/02/2024	Description of listings of AEs of participants who died, who had serious AEs and who discontinued study removed, description of listing of AEs leading to death added.	YES	Decided that these listings are redundant, to present AEs leading to death will be more suitable.
4.2.2.3	19/02/2024	Clarified that outputs of SARS-CoV-2 Neutralizing Antibody assessments will be presented separately for each dominant variant	YES	Clarification
4.2.3.3	19/02/2024	Clarification of table of symptomatic COVID-19 cases.	YES	Clarification
4.3.1.2	19/02/2024	Presentation of cases of IP administration interruption	YES	Clarification
4.3.3.2	19/02/2024	Description of shift tables for blood parameters updated: the table will be based on maximum CTCAE grades separately for low and high abnormal results	YES	Such presentation of abnormal results is more informative and suitable.
4.3.4.1	19/02/2024	The rules of dealing with multiple VS measurements added.	YES	Clarification
4.3.5.2	19/02/2024	Description of listing of physical examination removed.	YES	Physical examination findings register and present as AEs
5	19/02/2024	The rule of selecting data for the interim analysis added. Typos corrected	YES	Clarification
3.3.1	24/06/2024	The rule of rounding log-transformed data is added	YES	Clarification
4.1.5.1	24/06/2024	Presentation of number of participants previously vaccinated is added	YES	Clarification
4.2	24/06/2024	Typos in section numbers in the table were corrected	YES	Clarification

CSP – clinical study protocol; NA – not applicable; SAP – statistical analysis plan.

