3.3.2 Visit Window

Period	Visit	Nominal Day	Windows			
			SARS-CoV-2 serology	SARS-CoV-2 nAb serum samples	Laboratory assessments	Vital signs
Screening	Screening	(-7) – (-1)	(-7) – (-1)	(-7) – (-1)	(-7) – (-1)	(-7) – (-1)
Treatment and Follow-up Period	Visit 1	1	1	1	1	1
	Visit 2	8	–	5 – 11	2 – 18	2 – 94
	Visit 3	15	–	12 – 18	–	–
	Visit 4	29	2 – 60	26 – 32	19 – 195	–
	Visit 5	91	61 – 136	86 – 96	–	–
	Visit 6	181	137 – 195	167 – 195	–	95 – 195

When one or more results are available for the same visit window, the result with the date closest to the expected visit date will be used in the analysis. If two observations are equidistant from the expected visit date, the later observation will be used in the analysis. Visits outside the specified visit windows will not be part of the by-visit summaries (i.e., no mapping will be applied to such data points).

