3.3.3 Handling of Unscheduled Visits

Unscheduled, retest (with the same visit number assigned), and early discontinuation measurements will be included in by-visit summaries per Section 3.3.2

In the case of a missing value at a scheduled visit, which is then followed by a non-missing value at an unscheduled assessment within the same visit window, the non-missing value at the unscheduled assessment will be used.

Data collected at unscheduled assessments might be included in baseline definitions, and in any definitions of maximum value, minimum value where appropriate.

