4.3.4.2 Presentations

Vital signs will be summarized following a similar procedure as described above for laboratory values. Will be assessed and presented in Safety analysis set in summary tables using descriptive statistics for continuous variables. Changes from baseline will be summarized over all participants by treatment arm and visit. A listing of all vital signs will be provided.

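### SAP 4.3.4.1 and SAP 3.3.2 give different rules for choosing among several vital-sign readings in one visit window, and neither says which prevails

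*SAP*

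**What the plan says.** **General rule.** SAP 3.3.2 sets analysis windows by type of assessment. For vital signs they are Days 2-94 for Visit 2 (nominal Day 8) and Days 95-195 for Visit 6 (nominal Day 181). Where a window holds several results, "the result with the date closest to the expected visit date will be used in the analysis". For ties: "If two observations are equidistant from the expected visit date, the later observation will be used in the analysis".

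**Extra readings.** SAP 3.3.3 brings them under that rule: "Unscheduled, retest (with the same visit number assigned), and early discontinuation measurements will be included in by-visit summaries per Section 3.3.2". It adds that, when the scheduled value is missing, a later unscheduled value in the same window takes its place.

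**Vital-sign rule.** SAP 4.3.4.1 states: "For multiple VS assessments on Visits 2 and 6 the earliest assessment within a visit window will be used for analysis". It does not refer to Section 3.3.2. The SAP's amendment history dates it to 19/02/2024, as a clarification: "The rules of dealing with multiple VS measurements added". The log lists no change to Section 3.3.2 or 3.3.3 on that date or later.

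**Outputs.** SAP 4.3.4.2 plans summaries by visit and adds: "Changes from baseline will be summarized over all participants by treatment arm and visit". It also says: "A listing of all vital signs will be provided".

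**The concern.** The two sections use different criteria for the same data. One looks for the reading nearest the planned day and prefers the later of two equals; the other takes the first reading in the window. Section 3.3.2 has no exception clause, although Sections 3.3 and 3.3.1 reserve exceptions to their own defaults.

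The windows are wide. They work with a nearest-day rule, because a distant reading is used only when nothing nearer exists. Under a first-in-window rule the same width lets a distant reading displace one taken on the planned day. Two programmers who each follow the SAP could therefore report different vital-sign values and changes from baseline, and a row labelled Visit 6 could hold a reading taken weeks earlier.

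**Working it through.** **Inputs**
- Nominal days 8 and 181: SAP 3.3.1 and 3.3.2.
- Vital-sign analysis windows, Days 2-94 and 95-195: SAP 3.3.2.
- Protocol visit windows: Visit 2 ± 3 days (Days 5-11) and Visit 6 ± 14 days (Days 167-195), from Protocol Table 1.
- Planned arm sizes 87 and 29: Protocol synopsis.

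**The SAP's windows reproduced.** The midpoint of the nominal days is (8 + 181)/2 = 94.5, so the boundary falls between Days 94 and 95. The upper limit is 181 + 14 = 195. Both match the table, so the early opening of the Visit 6 window follows from midpoint windowing.

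**How early a Visit 6 value can be.** From the nominal day: 181 − 95 = 86 days. From the earliest permitted Visit 6 day: 167 − 95 = 72 days.

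**Both rules applied to pairs of readings**

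| Window | Reading days | 3.3.2 selects | 4.3.4.1 selects |
|---|---|---|---|
| Visit 6 | 95 and 181 | 181 | 95 |
| Visit 6 | 120 and 181 | 181 | 120 |
| Visit 6 | 178 and 184 (tied) | 184 | 178 |
| Visit 6 | 181 and 190 | 181 | 181 |
| Visit 2 | 3 and 8 | 8 | 3 |
| Visit 2 | 5 and 11 (tied) | 11 | 5 |
| Visit 2 | 8 and 60 | 8 | 8 |

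**Which extra readings split the rules**
- Visit 6, with a Day 181 reading present: an extra reading on Days 95-180 splits them (180 − 95 + 1 = 86 days). One on Days 182-195 does not.
- Visit 6, with a reading anywhere in Days 167-195: an extra reading on Days 95-166 always splits them (72 days), because it lies at least 181 − 166 = 15 days out and the other at most 14.
- Visit 2, with a Day 8 reading present: only Days 2-7 split them (6 days).
- Visit 2, with a reading anywhere in Days 5-11: Days 2-4 always split them and Days 12-94 never do.

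These are counts of calendar days, not of participants. The Visit 6 lines also presuppose that a vital-signs reading is taken at Visit 6.

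**Size in a table (assumption, not in the documents).** Suppose one participant is affected and the two candidate readings differ by d units. The arm mean shifts by d/n:

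| d | n = 29 | n = 87 |
|---|---|---|
| 5 | 5/29 = 0.17 | 5/87 = 0.06 |
| 10 | 10/29 = 0.34 | 10/87 = 0.11 |
| 20 | 20/29 = 0.69 | 20/87 = 0.23 |

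**The Schedule.** In the text copy of Protocol Table 1 the later vital-signs tick stands under Visit 5 (Day 91 ± 5, Days 86-96) and Visit 6 has none, whereas the SAP uses Visits 2 and 6. The columns may have shifted in conversion. If the tick does belong to Visit 5, Days 86-94 (9 of the 11 permitted days) fall in the SAP's Visit 2 window. With a Visit 2 reading present, both rules would then choose that reading, and the Visit 5 reading would not appear in the by-visit table.

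**The case against.** **The sections can be read as complementary.** Section 4.3.4.1 is specific to vital signs, was added later, and follows rules for repeat readings at Visit 1. On that reading Section 3.3.2 picks the date and Section 4.3.4.1 picks among repeats on that date. This may well be what was meant. The text, however, refers to the visit window and not to the day, and those windows span 93 and 101 days.

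**Section 3.3.3 points against displacement.** Its sentence on missing scheduled values suggests that unscheduled readings fill gaps and do not replace a scheduled value that exists. That is fair evidence of intent. It is not a precedence rule, and the same section sends all unscheduled readings into the windows.

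**Same-day repeats.** A reader might infer that the rules always clash when a reading is repeated on the same day. That requires the tie rule to cover two readings on one date. It can equally be read as covering two dates on either side of the visit day, and Section 3.3.2 would then be silent on same-day repeats. The protocol's requirement, "Any abnormal vital signs must be repeated after the participant has been at rest for at least 5 minutes", sits in a footnote attached to Visit 1, which has its own selection rule. Whether it extends to later visits is not stated.

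**Visit 6 versus Visit 2.** The day counts might suggest that nearly all of the effect falls at Visit 6. The documents do not support that: they give no frequency of extra readings, early unscheduled readings could be the commoner ones, and the Schedule leaves open whether vital signs are taken at Visit 6.

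**Conclusion.** Minor, but wrong as written. Two sections of the SAP prescribe different selections for the same vital-sign data, and neither is given precedence. Read literally, Section 4.3.4.1 allows a Visit 6 value from up to 86 days before Day 181. Section 3.3.3 suggests this was not intended but does not rule it out. The conflict over readings on different days holds on the literal text; the conflict over same-day repeats holds only if the tie rule covers two readings on one date.

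The effect is confined to descriptive by-visit values and changes from baseline, for participants with more than one reading in a window. Its frequency, and its split between Visits 2 and 6, cannot be derived from the documents. The mean shifts shown rest on an assumed difference between readings. Every reading is listed, no hypothesis test is planned, and the AE, SAE, MAAE and AESI endpoints are unaffected.

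A reader might also take the Day 95 opening of the Visit 6 window as an error in itself. It is not: it follows from the midpoint of Days 8 and 181, and causes difficulty only when combined with a first-in-window rule.

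**What to change.** Check Protocol Table 1 first: is the later vital-signs assessment at Visit 5 or at Visit 6? If it is at Visit 5, the Schedule and the SAP's vital-sign visits and windows must be reconciled before anything else is settled. If it is at Visit 6, the windows can stay.

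Then replace the last sentence of the multiple-assessment rules in SAP 4.3.4.1 with:

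> *For visits after Visit 1, the assessment day is selected by the closest-date rule in Section 3.3.2; if several readings exist on the selected day, the earliest is used, and this same-day rule takes precedence over the tie rule in Section 3.3.2.*

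This keeps the nearest-day logic that the windows were built for, leaves the tie rule in force for two different dates, and settles same-day repeats in one direction.

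The cost is one SAP paragraph and one look at the Schedule, with no new assessments. Further edits arise only if the Schedule and the SAP prove to differ.

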4.3.4.2 Presentations

Vital signs will be summarized following a similar procedure as described above for laboratory values. Will be assessed and presented in Safety analysis set in summary tables using descriptive statistics for continuous variables. Changes from baseline will be summarized over all participants by treatment arm and visit. A listing of all vital signs will be provided.

4.3.5 Electrocardiogram and Physical Examination

4.3.5.1 Definitions and Derivations

Electrocardiogram (ECG) and physical examination will be conducted on the screening and during the study if indicated.

4.3.5.2 Presentations

A listing of ECG data will be provided.

4.3.6 Liver Signs and Symptoms

4.3.6.1 Presentations

The following laboratory data on liver toxicity for each treatment arm will be provided in the Safety Analysis Set:

- A table for the highest recorded values of alanine aminotransferase (ALT) and aspartate aminotransferase (AST) after baseline, grouped into the following

categories: less than 3 times the upper limit of normal (ULN), from 3 up to but not including 5 times the ULN, from 5 up to but not including 10 times the ULN or 10 times or greater than the ULN. These values will be cross-referenced with the highest recorded total bilirubin (TBL) values post-baseline, categorized as less than 2 times the ULN or 2 times the ULN and above.

- A listing of participants who had at least one recorded post-baseline value of ALT or AST 3 times the ULN or greater or a TBL value 2 times the ULN or greater
- A listing of participants who had at least one recorded post-baseline value of ALT or AST 3 times the ULN or greater and simultaneously a TBL value 2 times the ULN or greater

5 INTERIM ANALYSIS

Two planned statistical analyses will be performed:

Interim analysis (unblinded and performed by a separate unblinded team)

An interim analysis is planned after 116 participants have completed Visit 4 (Day 29) (or early withdrawal from the study) to evaluate early safety at Day 29. All available data by the date when the last participant completed (or withdrew from) Visit 4 will be included in the interim analysis. Efficacy data may be presented as appropriate at interim analysis if adequate data allows.

This interim analysis will include primary endpoint variables: all AEs, SAEs, MAAEs, and AESIs. If available, nAb responses to the SARS-CoV-2 emerging dominant variant(s) will be analysed.

This interim analysis will be unblinded and will be performed by a separate unblinded team. Disposition, demographic, baseline characteristics, occurrence of AEs collected through the study and occurrence of SAEs, MAAEs, and AESIs collected throughout the study will be provided by treatment arms.

Final analysis (unblinded)

The final analysis will be performed once all participants complete Visit 6 (Day 181) or early withdrawal from the study.

No multiplicity correction is expected as there are no formal statistical tests planned, only descriptive data.

APPENDIX A MISSING MEDICATION DATES IMPUTATION

The imputation rules for missing or partial medication start/stop dates are as follows:

- Missing or partial medication start dates:
 - If only the day is missing, use the first day of the month.
 - If both the day and month are missing, use the first day of the year.
 - If only the month is missing, use the year's first month.
 - If day and month are present and the year is missing, use the year of the informed consent date.
 - Use the informed consent date if the day, month, and year are missing.
- Missing or partial medication end dates:
 - Use the earliest of the data cutoff date and the end-of-study date as the reference date for the imputation rules below.
 - If the year is the same as the reference date's year:
 - If the day is missing and the month is the same as the reference date's month, use the day of the reference date.
 - If the day is missing and the month is different from the reference date's month, use the last day of the month.
 - If the day is present and the month is missing, use the month of the reference date.
 - If the year is different from the reference date's year:
 - If only the day is missing, use the last day of the month.
 - If both the day and month are missing, use the last day of the year.
 - If the date is completely missing, use the reference date.

APPENDIX B MISSING SAFETY DATA

Missing safety data is generally not imputed. However, safety assessments of the form of “ $<x$ ” (ie, below the lower limit of quantification [LLOQ]) or “ $>x$ ” (ie, above the upper limit

of quantification [ULOQ]) are imputed as “x” in the calculation of summary statistics but are displayed as “ $<\!x$ ” or “ $\!>x$ ” in the listings.

APPENDIX C MISSING DATA ON NEUTRALIZING ANTIBODIES

The analysis of GMTs will use the following imputation methods:

- Missing titer values will not be imputed.
- Titer values measured below the LLOQ will be imputed with half the LLOQ in summaries and analyses but will be listed as reported in the raw data listings.
- Titer values measured above the ULOQ will be imputed at the ULOQ value.

[figure not shown]

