3.2 Analysis Populations

The following populations are defined:

Table 1 Populations for Analysis

Population/Analysis set	Description
Screened Set	All participants who provided the Informed Consent
Full analysis set (FAS)/ Safety analysis set	All randomized participants who received part or all of study intervention. Participants in the FAS will be classified according to the assigned treatment. The safety analysis set will include participants from the FAS but report participants according to the actual treatment received regardless of the assigned treatment.
SARS-CoV-2 neutralizing antibody analysis set	All participants in the FAS with baseline and post-dose antibody measurements (i.e. at least one post-dose antibody measurement with a measurable SARS-CoV-2 titer in serum). Participants will be classified according to the actual received treatment. Participants with protocol deviations that may interfere with generation or interpretation of an antibody response may be excluded or have data collected after the protocol deviations set to missing.

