4.2.2.2 Derivations

The geometric means will be calculated as the mean of the assay results after taking the logarithm transformation and then anti-logarithm transformation the mean to express results on the original scale. Two-sided 95% CIs will be obtained by taking log transforms of assay results, calculating the 95% CI with reference to Student's t-distribution, and then anti-logarithm transforming the confidence limits.

Geometric mean fold rises (GMFRs) will be reported and limited to participants with non-missing values at both time points.

Dealing with missing and undetectable results (<LLOQ and >ULOQ) described in Appendix C. Participants who experience an important protocol deviation that can interfere with an antibody response or violate adherence to the assigned dose, become infected, receive COVID-19 treatment or vaccination that can alter nAb levels will have data collected after the intercurrent event set to missing for analysis of this endpoint (i.e., while-on-treatment strategy is applied).

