4.2.2.3 Analysis

GMT and GMFRs, corresponding gSD, 2-sided 95% CIs, minimum and maximum will be presented for each visit by treatment arm in tables separately each dominant variant of SARS-CoV-2. Also box and whiskers plots (separately for each dominant variant) will be presented in the following manner: dots show geometric means, lines within boxes are medians, box bounds are quartiles and whiskers are minimums and maximums.

Also all data will be presented in listings.

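### Titers above the ULOQ are set to the ULOQ and analysed as measured, which lowers the GMT and narrows its CI by an amount that depends on a share the SAP does not plan to report; LLOQ/2 also distorts, in a direction that depends on titer spread

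*SAP*

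**What the plan says.** SAP Appendix C has three rules for neutralizing antibody titers. Absent results are left alone: "Missing titer values will not be imputed". At the lower limit, "Titer values measured below the LLOQ will be imputed with half the LLOQ in summaries and analyses". At the upper limit, "Titer values measured above the ULOQ will be imputed at the ULOQ value".

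SAP 4.2.2.2 points to that appendix ("Dealing with missing and undetectable results (<LLOQ and >ULOQ) described in Appendix C") and then treats the completed data as ordinary measurements: "Two-sided 95% CIs will be obtained by taking log transforms of assay results", followed by "calculating the 95% CI with reference to Student's t-distribution, and then anti-logarithm transforming the confidence limits". GMFRs use participants with values at both time points. SAP 4.2.2.3 fixes the output: "GMT and GMFRs, corresponding gSD, 2-sided 95% CIs, minimum and maximum will be presented for each visit by treatment arm", separately for each dominant variant, with box plots and listings.

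SAP 4.2.2 and Appendix C contain no method for censored titers, no sensitivity analysis for this endpoint, and no tabulated count of substituted values. The protocol (8.5.2 and 9.4.2.2) does not address out-of-range titers. Neither document gives the LLOQ, the ULOQ or the expected share of samples outside them.

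**The concern.** A titer reported as above the ULOQ is known only to exceed that limit. Replacing it with the limit discards the excess, and giving many samples one identical value removes real spread. The interval is then centred too low and made too short. The arm most exposed is AZD3152, where a 300 mg dose of neutralizing antibody may push some titers past the assay ceiling.

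Half the LLOQ is likewise a guess about where unseen values lie. It enters the GMT directly and, when a baseline is below the limit, the denominator of the fold rise.

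Protocol 4.2 treats neutralizing activity as the surrogate for efficacy, and Protocol 2.1 says the study is legally required for marketing authorization in Russia. Because the analysis is descriptive, the GMT, the GMFR and their intervals are the whole result for this endpoint. A nominal 95% interval that covers much less often would mislead about both size and precision.

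**Working it through.** **Inputs from the documents.** Arm sizes are 87 and 29 (Protocol 1.1, Number of Participants), consistent with 116 randomized 3:1: 116 × 3/4 = 87 and 116 × 1/4 = 29. The substitution rules are in SAP Appendix C and the t-interval on log titers in SAP 4.2.2.2. The plan states no figure for titer bias or interval width, so there is none to reproduce.

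**Assumptions.** Log titers are normal; the SD and the share f outside the range are varied. Full arm sizes are used; fewer evaluable samples at a visit would soften the loss of coverage for a given bias.

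**Direction under the ULOQ rule.** The analysed value is min(y, U). It never exceeds y, so the mean log titer cannot rise. Two capped values are never further apart than the originals, so the sample SD cannot rise. This holds for any titer distribution.

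**Size under the ULOQ rule.** Let u be the standard normal quantile at 1 − f and φ the normal density. In SD units, the bias of the mean log titer is −φ(u) + f·u. At f = 0.20, u = 0.842 and φ(u) = 0.280, so the bias is −0.280 + 0.168 = −0.112. A log10 SD of 0.5 is 0.5 × 2.303 = 1.151 on the ln scale, so the GMT ratio to truth is exp(−0.112 × 1.151) = 0.88.

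The SD of capped values is 0.83 of the true SD. The shift in standard errors is 0.112 × √87 / 0.83 = 1.25. With t(86) = 1.99, coverage is about Φ(1.99 − 1.25) = 77%; simulation gives 79%.

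| Share above ULOQ (n=87, log10 SD 0.5) | GMT ratio to truth | CI width ratio | Coverage |
|---|---|---|---|
| 1% | 1.00 | 0.99 | 95% |
| 5% | 0.98 | 0.96 | 94–95% |
| 10% | 0.95 | 0.92 | 93% |
| 20% | 0.88 | 0.83 | 79% |
| 30% | 0.80 | 0.75 | 35% |

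Width ratio compares with the interval from uncensored data, on the log scale. Under this rule the SD cancels from the width ratio and the coverage, so those columns depend on f, n and normality only. The GMT ratio does depend on spread: at 30% above, it runs from 0.88 to 0.68 as the SD of ln titer goes from 0.7 to 2.0.

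**LLOQ/2 rule.** Let l be the normal quantile at f and s the SD of ln titer. The bias in SD units is φ(l) + f·(l − ln 2 / s). The ln 2 term is a jump at the limit, so neither the sign nor the change in width is fixed. At f = 0.30, l = −0.524 and φ(l) = 0.348:

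- Log10 SD 0.2 (s = 0.461): 0.348 + 0.3 × (−0.524 − 1.505) = −0.261; GMT ratio exp(−0.261 × 0.461) = 0.89.
- Log10 SD 0.6 (s = 1.382): 0.348 + 0.3 × (−0.524 − 0.502) = 0.040; GMT ratio exp(0.040 × 1.382) = 1.06.

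| n=29 | GMT ratio to truth | CI width ratio | Coverage |
|---|---|---|---|
| SD 0.2, 30% below | 0.89 | 1.30 | 83% |
| SD 0.3, 50% below | 0.93 | 1.00 | 90% |
| SD 0.4, 50% below | 1.02 | 0.88 | 95% |
| SD 0.6, 30% below | 1.06 | 0.91 | 95% |
| SD 0.6, 50% below | 1.23 | 0.78 | 88% |
| SD 0.6, 70% below | 1.65 | 0.59 | 1% |

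Setting the bias to zero gives the break-even spread s = f·ln 2 / (φ(l) + f·l): log10 SD 0.47 at 30% below and 0.38 at 50% below. Narrower titers give a GMT that is too low, wider ones a GMT that is too high.

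**GMFR.** Errors in numerator and denominator divide. With 20% of post-dose values above ULOQ (0.88) and half of baselines below LLOQ, baseline log10 SD 0.6 gives 0.88 / 1.23 = 0.72, 28% too low; simulated coverage is about 43–44% (n=87, baseline and post-dose independent). With baseline log10 SD 0.2 the ratio is 0.88 / 0.85 = 1.03. Capping alone lowers the fold rise, but the net error can change sign.

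**Censored-normal maximum likelihood** on the same kind of data, in seven cells (10, 30 and 50% above ULOQ at n=87; 30 and 50% below LLOQ at n=29, the latter at three spreads), gave GMT ratios of 0.99–1.01 and coverage of 94–97%. The data were generated from the model being fitted, so this is the favourable case.

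**The case against.** Several objections stand.

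- **The harm is conditional.** No passage shows that either tail is heavily populated, and at 10% above the ULOQ the loss is small. A reader might infer that the GMTs will be biased and every interval too narrow; the documents do not support that.
- **The lower limit has no fixed direction.** A reader might infer that the placebo GMT will be overstated with a falsely tight interval. That needs a wide titer spread. The analysis set also requires "at least one post-dose antibody measurement with a measurable SARS-CoV-2 titer in serum", which removes participants with no measurable post-dose titer before Appendix C applies and makes very high shares below LLOQ less plausible. Nor must the population be antibody-poor: obesity, COPD or heart failure alone qualifies (Protocol 5.1), and vaccination or infection more than 6 months earlier is allowed (Protocol 5.2).
- **Censoring is partly visible.** Values below LLOQ are listed as reported, and the minimum, maximum and box plots are shown. With more than 25% at the ULOQ the upper quartile meets the maximum, and the plotted median is unaffected while less than half the values are censored. It would be wrong to say the reader cannot detect the problem; a count beside the GMT is simply much clearer.
- **The stakes are limited.** The endpoint is secondary, SAP 3.3.4 rules out hypothesis testing, and no sample size depends on these intervals. Capping the active arm's post-dose titers works against the product.
- **Likelihood is not a cure-all.** In a two-group titer mixture (30% low responders, means 1 log10 apart, 30% below LLOQ, n=29) both methods were about 11% too high. Making likelihood the main estimator whenever a cell passes a threshold would mix methods across visits and arms.

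What these leave untouched is that the ULOQ rule has a certain direction, the SAP offers no check on its size, and no table shows how often either rule was used.

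**Conclusion.** The point holds in conditional form. Treating ULOQ-capped titers as measured biases the GMT down and narrows its CI whenever any titer exceeds the limit; capping post-dose values alone pulls the GMFR down too. The effect is negligible at 1% above, small up to about 10% (coverage about 93%) and serious from about 20% (coverage about 79%, GMT 12% low). These sizes assume normal log titers and n=87; the GMT figure also assumes log10 SD 0.5. LLOQ/2 distorts GMT, GMFR and interval in a direction set by the titer spread. Since the limits, shares and spread are not in the documents, nothing here shows that the trial's results will be wrong. This is a cheap improvement that lets readers judge how far each GMT and interval can be trusted.

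**What to change.** - **SAP 4.2.2.3:** print n (%) below LLOQ and n (%) above ULOQ beside each GMT and GMFR, by arm, visit and variant. For GMFR, count baseline and post-dose values separately.
- **SAP 4.2.2.2 and Appendix C:** keep the substitution rules as the main analysis. Add a sensitivity analysis that estimates the mean log titer and its 95% CI by maximum likelihood for a normal distribution censored at LLOQ and ULOQ, with an interval-censored analogue for log fold rise.
- **Sparse cells:** where nearly all values in a cell are censored, show the counts only.

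The counts cost almost nothing. The sensitivity analysis needs somewhat more programming, chiefly for fold rise when both values may be censored. It relies on a lognormal assumption, and some intervals will be wider than under substitution. No change to data collection, sample size or the main tables' estimator is needed.
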